17.1 Sample size calculation

The sample size calculation is based on the objective to detect a difference in the time to inadequate glycaemic control between the Victoza[®] arm and the OAD arm, using a two-sided log rank test at a 5% significance level. The power is set to 90%.

The distributions of event time for the two treatment arms are derived from a model of the continuous HbA_{1c} measurements. In this model, the post-baseline measurements for each subject are assumed to be normally distributed and, conditional on a random subject effect, independent between assessment times. Based on data from another Novo Nordisk trial (NN2211-1860), the mean HbA_{1c} in the Victoza[®] arm is anticipated to be at a constant post-baseline level of 6.9% and the standard deviation of the within-subject error is anticipated to be 0.85%. The latter is in reality an estimate of the standard deviation of the total error and is therefore a conservative estimate of the within-subject standard deviation.

A mean treatment difference in HbA_{1c} of 0.3% is considered clinically relevant and is therefore used as the assumption in the model¹⁸. The HbA_{1c} levels in the two treatment arms are assumed to diverge after the visit at 65 weeks, when the mean in the OAD arm is assumed to increase in one step from 6.9% to 7.2%. Otherwise, the means are assumed to be constant during the observation period between 26 and 104 weeks.

Based on previous trials, the anticipated percentage of subjects who discontinue treatment prematurely (are withdrawn from the trial) without having inadequate glycaemic control is 20% in both treatment arms. As a conservative assumption, these subjects are assumed to discontinue before the week 26 visit and thus not give any contribution to the statistical analysis.

Based on the assumptions above, the required sample size is found to be 1994 subjects. The anticipated percentage of subjects who have had inadequate glycaemic control after 104 weeks is 66% in the Victoza[®] arm and 76% in the OAD arm. The number of subjects who complete the trial

Protocol		Date:	04 September 2015	Novo Nordisk
Trial ID: NN2211-4232	CONFIDENTIAL	Version:	1.0	
UTN: U1111-1170-7035	CONFIDENTIAL	Status:	Final	
EudraCT no.: 2015-002417-29		Page:	48 of 67	

without premature treatment discontinuation (for any reason including inadequate glycaemic control) is expected to be 462.

In order to investigate the influence of the values of the model parameters on the calculation, sample sizes have been calculated for different alternative scenarios, assuming the mean post-baseline HbA_{1c} level in the Victoza[®] arm to be 6.8%, 6.9% or 7.0%, the standard deviation to be 0.7% or 0.85%, the treatment difference to be 0.2% or 0.3% and the divergence time to be 52 or 65 weeks. The results are presented in Table 17–1 with the adopted sample size marked in bold.

Table 17–1 Sample size calculations for different scenarios – total number of randomised subjects

		Divergence	time		
		52 weeks		65 weeks	
		Standard de	viation	Standard d	eviation
Mean HbA _{1c} in Victoza [®] arm	Treatment difference	0.7%	0.85%	0.7%	0.85%
6.8%	0.2%	1138	1782	2394	3840
	0.3%	492	776	1010	1636
6.9%	0.2%	1332	2042	2948	4608
	0.3%	588	902	1272	1994
7.0%	0.2%	1668	2456	3948	5868
	0.3%	752	1098	1736	2566

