1 Introduction including rationale for the protocol amendment

The reason for initiating this protocol amendment is that the current protocol text on drug accountability does not allow the subjects to keep unused and partly used trial product during the trial. In this trial the trial products are handed out by pharmacies or similar. Since some subjects may not be able to collect new trial product from the pharmacy on the same day as they attend a site visit and hand in the trial product that were prescribed at the previous site visit, this means that these subjects may risk being without trial product for one or more days unless the current protocol text on drug accountability is changed. Therefore, the protocol text regarding drug accountability has been revised as described below.

This protocol amendment will include new wordings in order to prevent potential cases of patients using trial products that have exceeded the expiry date. In addition this amendment will include clarifications of the randomisation ratio, sample size calculation and specific statistical analyses in line with suggestions from FDA.

Columbia has been included in the trial after the finalisation date of protocol version 1.0 and therefore country specific issues for Columbia has been added.

Finally, this protocol amendment will include updates and clarifications to wordings that may be confusing in their current form. This includes removal of a sentence in protocol section 6.7, rewording of section 8.2.1, updating figure 12.1 describing the initial reporting of AEs to align this with the remaining text in the protocol and other minor changes.

In this protocol amendment:

- Any new text is written *in italics*.
- Any text deleted from the protocol is written using strike through.

2 Changes

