2.11 Section 17.1 Sample size calculation

Based on the assumptions above, the required sample size is found to be 1994 subjects. The anticipated *number* percentage of subjects who have had inadequate glycaemic control after 104 weeks is 526 66% in the Victoza[®] arm and 606 76% in the OAD arm. *In each arm, 200 subjects are expected to discontinue treatment prematurely without having inadequate glycaemic control.* The number of subjects who complete the trial without premature treatment discontinuation (for any reason including inadequate glycaemic control) is expected to be 462.

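### Protocol 17.1 names a random subject effect but gives it no variance, and its stated power, event rates and completers fit together only if that variance is essentially zero

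*Protocol*

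**What the plan says.** Protocol section 17.1 derives the event-time distributions from a model of continuous HbA1c. Values are normal and, "conditional on a random subject effect, independent between assessment times". The Victoza mean is constant at 6.9%. The OAD mean steps from 6.9% to 7.2% after week 65. For the spread, "the standard deviation of the within-subject error is anticipated to be 0.85" percent, but the next sentence says this value "is in reality an estimate of the standard deviation of the total error and is therefore a conservative estimate of the within-subject standard deviation".

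The stated results are 1994 randomised subjects for 90% power with a two-sided 5% log rank test, and 462 completers (also in section 6.1). On events: "The anticipated percentage of subjects who have had inadequate glycaemic control after 104 weeks is 66% in the Victoza" group; the corresponding OAD figure is 76%. Table 17-1 is introduced with the words "In order to investigate the influence of the values of the model parameters on the calculation". It varies the Victoza mean, the SD, "the treatment difference to be 0.2% or 0.3% and the divergence time to be 52 or 65 weeks".

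Amendment 1 announces "clarifications of the randomisation ratio, sample size calculation and specific statistical analyses". In its item 2.11 it replaces the percentages with 526 and 606 events and adds: "In each arm, 200 subjects are expected to discontinue treatment prematurely without having inadequate glycaemic control".

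None of these places, nor the SAP, gives a between-subject variance, an ICC or a correlation between visits.

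**The concern.** An event needs two consecutive values above 7.0%, so its probability depends on how strongly a subject's values are correlated. A model with a random subject effect needs two variances, and the plan gives one. It then moves the whole of the total variance into the within-subject term and describes this as conservative.

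That description presupposes some between-subject variance; otherwise the total and within-subject SDs would be equal. If such variance exists, it should also enter the calculation as the subject effect. There it works against the trial. Correlated values bring a larger share of the events forward to before week 65, when the arms are assumed identical, and the later 0.3% step then produces fewer extra events.

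At stake are the stated power for the sole primary endpoint, the expected events per arm and the expected completers. A reader of a non-significant result would take the risk of a missed effect to be 10%, without knowing that this figure rests on an unstated value.

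**Working it through.** **Inputs.** From protocol 17.1: means 6.9% and 7.2% with divergence after week 65, SD 0.85%, and 20% per arm lost before week 26 with no contribution. From protocol 17.3 and the SAP's primary endpoint section: two consecutive values above 7.0% at weeks 26, 38, 52, 65, 78, 91 and 104. Allocation is 1:1 (Amendment 1). Evaluable per arm: 1994/2 × 0.8 = 797.6.

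**Event distribution with zero subject variance.** The probability of a value above 7.0% is p = 1 − Φ(0.1/0.85) = 0.453, and 1 − Φ(−0.2/0.85) = 0.593 in the OAD arm at weeks 78, 91 and 104. Let A and B be the probabilities of being event-free with the last value low or high. At each visit k:

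- event at k = B(k−1) × p(k)
- B(k) = A(k−1) × p(k)
- A(k) = [A(k−1) + B(k−1)] × [1 − p(k)]

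| Week | 38 | 52 | 65 | 78 | 91 | 104 | Total |
|---|---|---|---|---|---|---|---|
| Victoza | 0.205 | 0.112 | 0.112 | 0.089 | 0.077 | 0.064 | 0.6598 |
| OAD | 0.205 | 0.112 | 0.112 | 0.117 | 0.131 | 0.082 | 0.7595 |

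**Reproducing the plan.**

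- Events: 797.6 × 0.6598 = 526.3 and 797.6 × 0.7595 = 605.8 (stated 526 and 606).
- Completers: 1994 − 400 − 526 − 606 = 462 (stated 462).
- Log rank score, summing over visits OAD events minus D × Y1/Y: E = 48.77. Tie-corrected variance, summing D × (Y0 × Y1/Y²) × (Y − D)/(Y − 1): V = 229.94. Here D is the number of events at a visit, Y0 and Y1 are the numbers at risk per arm, and Y is their sum.
- E/√V = 3.216, so power is Φ(3.216 − 1.960) = 89.5%. Simulation gives 90.2%.
- N for 90% power: 1994 × (3.2415/3.216)² = 2026 (stated 1994, +1.6%).
- All 24 cells of Table 17-1 reproduce within −0.8% to +2.6%.

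**Splitting the 0.85%.** Take between-subject SD = 0.85 × √ICC and within-subject SD = 0.85 × √(1 − ICC), average the event distribution over the subject effect, and hold N at 1994:

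| ICC (assumed) | Events, Victoza/OAD | Completers | N for 90% | Power at 1994 | Victoza events by week 65 |
|---|---|---|---|---|---|
| 0 | 66%/76% | 463 | 2026 | 90% | 65% |
| 0.01 | 66%/76% | 468 | 2058 | 89% | 65% |
| 0.05 | 65%/74% | 486 | 2182 | 87% | 67% |
| 0.1 | 64%/73% | 506 | 2328 | 85% | 68% |
| 0.3 | 60%/68% | 573 | 2812 | 78% | 74% |
| 0.6 | 55%/63% | 653 | 3179 | 73% | 81% |

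The last column is the share of Victoza-arm events that fall before the assumed divergence. The 463 at ICC 0 uses unrounded counts.

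**How tightly the figures fix the variance.** Table 17-1 cells within 3%: 24 at ICC 0, 16 at 0.01 (between-subject SD 0.085%), 4 at 0.02 and 0 at 0.03. N stays within 3% of 1994 up to about ICC 0.009, and 66%/76% hold to the nearest percent up to 0.014. Power alone returns to about 90% near ICC 0.95, but with 387/461 events and 747 completers, so the set still does not match.

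**Other reading.** Keep 0.85% as the within-subject SD and add a between-subject SD of 0.2, 0.3 or 0.5. Power at 1994 is then about 85%, 80% or 65%.

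**Where the shortfall is small.** At N = 1994, power is at least 94% for ICC 0 to 0.95 with 52-week divergence, and at least 89.8% with total SD 0.7%. With no dropout it is 92%, 86% and 82% at ICC 0.1, 0.3 and 0.6.

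**The case against.** - *Nothing is miscalculated.* The plan's figures reproduce, and a zero-variance subject effect is a special case of the stated model. That is true. The fault is that the special case is unstated and conflicts with the reason given for using the total SD.
- *The plan calls the SD conservative, not the sample size.* Literally so, and a larger SD does raise N in Table 17-1 (1272 at 0.7%, 1994 at 0.85%). But the remark has a purpose in a sample size section only if it reassures about N. That reassurance holds only if the between-subject part is dropped: removing 10% of the variance altogether gives N of about 1800. Keeping that 10% as a subject effect gives 2328.
- *The tight limits partly reflect the formula's own offset.* It is 1.6% above 1994 at ICC 0. Measured against its own ICC-0 value, the 3% limit on N is reached near ICC 0.019, and all 24 cells stay within 3% at ICC 0.01. This stands, but moves the limit only from about 0.01 to about 0.02.
- *The power loss rests on assumed ICCs, and the plan is cautious elsewhere.* Both points stand. The base case takes the later divergence and has all dropouts contribute nothing. Table 17-1 also shows larger sensitivities: 1994 subjects give about 81% power if the Victoza mean is 7.0% and 57% if the difference is 0.2%. Those are disclosed; the correlation is not, and the caution elsewhere does not settle it.

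**Conclusion.** The concern holds. The stated power, events, completers and Table 17-1 are mutually consistent only with a between-subject variance of zero or close to it. The text names a random subject effect and justifies its SD in a way that requires that variance to be non-zero. For the adopted base case the figures therefore do not follow from the model as described.

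The size of the effect depends on an ICC that the documents do not give, and on reading 0.85% as a total to be split. On that reading the miss rate would be about 15% at ICC 0.1 and 22% at 0.3, against the implied 10%, and completers would be about 506 and 573 instead of 462. The shortfall largely disappears with 52-week divergence or an SD of 0.7%, but neither is the adopted case. Type I error, the primary test and the treatment estimates are not affected.

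**What to change.** In section 17.1, state the between- and within-subject SDs estimated from trial NN2211-1860. Using both, restate the power for 1994 subjects, the expected events per arm and the expected completers, and carry the last figure into section 6.1.

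If the split is not available, show power over a range of ICC for both the 52- and 65-week divergence, and add the correlation to the parameters varied in Table 17-1.

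In either case, add a sentence saying that entering the total SD as the within-subject SD, with no between-subject variance, does not make the sample size conservative.

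The cost is protocol wording and one recalculation. No extra subjects are needed for this correction. The drawback is that the stated base-case power is likely to look less favourable.

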17.2 Definition of analysis sets

The following analysis sets are defined in accordance with the ICH-E9 guideline.

FAS: includes all randomised subjects who have received at least one dose and have any post randomisation data. The statistical evaluation of the FAS will follow the intention-to treat principle and subjects will contribute to the evaluation "as randomised".

SAS: includes all subjects exposed to at least one dose of trial product. Subjects in the SAS will contribute to the evaluation "as treated".

Protocol Trial ID: NN2211-4232	CONFIDENTIAL	Date: Version:	04 September 2015 1.0	Novo Nordisk
UTN: U1111-1170-7035 EudraCT no.: 2015-002417-29		Status: Page:	Final 49 of 67	

Before data are locked for statistical analysis, a review of all data will take place. Any decision to exclude a subject or single observations from the statistical analysis is the joint responsibility of the trial statistician, the international trial manager and the medical specialist. Exclusion of data from analyses will be used restrictively and normally no data should be excluded from the FAS. The subjects or observations to be excluded, and the reasons for their exclusion must be documented and signed by those responsible before database lock. The subjects and observations excluded from analysis sets, and the reason for this, will be described in the clinical trial report.

17.3 Primary endpoint

The primary endpoint is the time to inadequate glycaemic control defined as $HbA_{1c} > 7.0\%$ (53 mmol/mol) at two scheduled consecutive visits after the first 26 weeks of treatment and up to 104 weeks. First possible occurrence is at week 38.

The time to inadequate glycaemic control will be compared between the Victoza[®] arm and the OAD arm using a two-sided nonparametric test at a 5% significance level. The test will be a generalised log rank test for interval censored failure time data¹⁹. The analysis will not be based on any model assumptions such as proportional hazards. The possible event times will be considered as a discrete set of time points corresponding to the scheduled visits. An alternative but technically equivalent model would be to view the event time as a continuous variable which can only be observed to lie in the interval between the visit when inadequate glycaemic control is established and the previous scheduled visit. Subjects who complete the trial without an event of inadequate glycaemic control will be censored after the last visit at 104 weeks, which means that the event time is only observed to be greater than 104 weeks. Subjects who discontinue treatment before 104 weeks without having an event of inadequate glycaemic control will be censored immediately after the last visit which they attended while on treatment. In particular, subjects changing antidiabetic drug after randomisation will be discontinued from the trial and in relation to the primary endpoint be considered as censored and not having had an event of inadequate glycaemic control.

The result of the log rank test will be presented as the asymptotic p-value obtained from a chisquare distribution. If the asymptotic p-value is not considered a valid approximation based on the Mantel-Fleiss criterion²⁰, then the exact p-value will be calculated.

17.4 Secondary endpoints

17.4.1 Supportive secondary endpoints

17.4.1.1 Efficacy endpoints

Time to premature treatment discontinuation (for any reason including inadequate glycaemic control)

Protocol Trial ID: NN2211-4232 UTN: U1111-1170-7035 EudraCT no.: 2015-002417-29

CONFIDENTIAL

Date: Version: Status: Page:

The time to premature treatment discontinuation will be analysed using the same type of generalised log rank test as for the primary endpoint with the difference that subjects who discontinue treatment before 104 weeks without having an event of inadequate glycaemic control will not be considered as censored but as meeting the endpoint. For these discontinued subjects, the event will be considered to have occurred in the interval between the last attended visit on treatment and the next planned visit.

Change from baseline in HbA_{1c} at 104 weeks or at premature treatment discontinuation

The change from baseline in HbA_{1c} will be evaluated using an analysis of covariance (ANCOVA) model where the last post-baseline measurement taken on treatment will enter as the dependent variable, treatment arm and country as factors and baseline HbA_{1c} as a covariate. The estimated differences between Victoza[®] and OAD will be presented together with the corresponding 95% confidence intervals and two-sided p-values.

To further describe the effects of Victoza[®] compared to OAD with respect to the change from baseline in HbA_{1c}, supportive analyses will be performed using a mixed model for repeated measurements (MMRM) where all post-baseline measurements taken on treatment will enter as the dependent variable, treatment arm as a factor and baseline HbA_{1c} as a covariate. The factor and the covariate will be nested within visit. An unstructured covariance matrix for the measurements within subject will be employed. From this analysis, the differences between Victoza[®] and OAD at different visits will be estimated.

The purpose of the MMRM analysis is to estimate the treatment effects that would have been observed if all subjects had remained on treatment and completed all visits, instead of dropping out. The analysis relies on the assumption that data are missing at random (MAR), which means that given the observed data, the events that lead to data being missing are independent of the unobserved data. This is a reasonable assumption also for subjects discontinuing treatment due to inadequate glycaemic control since it can be explained by the observed data obtained prior to discontinuation.

Categorical endpoints related to HbA1c

Secondary categorical efficacy endpoints are subjects who at 104 weeks or at premature treatment discontinuation achieve (Yes/No):

Protocol Trial ID: NN2211-4232 UTN: U1111-1170-7035 Evdrec T as : 2015 002417 20	CONFIDENTIAL	Date: Version: Status:	04 September 2015 1.0 Final	Novo Nordisk
EudraCT no.: 2015-002417-29		Page:	51 of 67	

- $HbA_{1c} \leq 6.5\%$
- $HbA_{1c} \le 7.0\%$ without weight gain
- $HbA_{1c} \le 7.0\%$ without treatment emergent severe hypoglycaemic episodes or BG confirmed symptomatic hypoglycaemic episodes
- $HbA_{1c} \le 7.0\%$ without weight gain and no treatment emergent severe hypoglycaemic episodes or BG confirmed symptomatic hypoglycaemic episodes

These endpoints will be analysed separately using the same type of logistic regression model. In the calculation of the responses, the last post-baseline measurements of HbA_{1c} and body weight which were taken on treatment will be used. The model will include treatment arm as a factor and baseline HbA_{1c} as a covariate. The results will be described by the odds ratio for the comparison of Victoza[®] versus OAD and the associated 95% confidence interval and two-sided p-value.

Other efficacy endpoints

The change from baseline at 104 weeks or at premature treatment discontinuation will be evaluated for:

- FPG
- Body weight
- BMI
- Systolic and diastolic blood pressure

These endpoints will be analysed using the same type of ANCOVA as for HbA_{1c} but with the baseline measurement of the corresponding endpoint as covariate instead of baseline HbA_{1c} . The corresponding supportive analyses to estimate treatment differences at different visits will also be performed.

BMI will be derived at each visit with a body weight measurement by using the body weight from the corresponding visit and the height measured at screening.

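### The supportive repeated-measures models omit country although the matching ANCOVAs adjust for it, and no reason is given; the gain from adding it is modest

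*Protocol*

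**What the plan says.** Protocol section 17.4.1.1 describes two analyses of change from baseline in HbA1c.

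- **ANCOVA.** This is the model "where the last post-baseline measurement taken on treatment will enter as the dependent variable", with "treatment arm and country as factors and baseline HbA_{1c} as a covariate".
- **Supportive MMRM.** All post-baseline on-treatment values enter as the response, with "treatment arm as a factor and baseline HbA_{1c} as a covariate" and an unstructured covariance matrix. "The factor and the covariate will be nested within visit": one factor and one covariate, so country is absent.

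For FPG, body weight, BMI and blood pressure the protocol uses the same type of ANCOVA, "but with the baseline measurement of the corresponding endpoint as covariate". Country therefore stays in those models. It then adds: "The corresponding supportive analyses to estimate treatment differences at different visits will also be performed". Those MMRMs inherit the structure without country. Section 17.4.1.2 refers pulse, amylase and lipase to the HbA1c methods, so they appear to follow the same pattern.

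The protocol gives no reason for the difference. Amendment 1 clarifies that the primary test adjusts for no covariates but leaves these models alone, and the US amendment concerns only pre-trial HbA1c. The SAP, which is a programming specification, does not restate the covariates of either model. Its section 3.2 does list country among the core variables carried in the analysis datasets.

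**The concern.** The sponsor adjusts for country in every efficacy ANCOVA, so it already regards country as worth adjusting for. The design supports that view: protocol section 9.2 and Amendment 1 together name nine countries, both arms follow local labels, and the investigator chooses the OAD. Leaving country out of the paired MMRM looks like an oversight.

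Two things are at stake, both small.

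- **Precision.** If country predicts HbA1c, omitting it makes the visit-wise differences slightly less precise than they could be.
- **Missing data.** Section 17.4.1.1 rests the MMRM on missingness being ignorable once the observed data are taken into account. Country is observed but is not in the model. Section 17.1 expects only 462 of 1994 subjects to complete, and 20% per arm to leave before week 26 without an event. The flow chart schedules only one post-baseline HbA1c before week 26, at week 16, so the model has little outcome history to account for those early losses.

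**Working it through.** **1. Reproduce the plan's sample size, to obtain the numbers on treatment by visit.** Inputs from protocol section 17.1: mean 6.9% in both arms, 7.2% in the OAD arm after week 65, SD 0.85%, visits treated as independent, 20% lost before week 26, 997 subjects per arm (1994/2).

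- Probability of a value above 7.0%: 1 - Φ((7.0 - 6.9)/0.85) = 0.453; for the OAD arm after week 65, 1 - Φ((7.0 - 7.2)/0.85) = 0.593.
- Applying the rule of two consecutive high values over weeks 26 to 104 gives events in 66.0% and 76.0%, as stated.
- Log rank sample size (1.960 + 1.282)² × V/U² = 1619, where U and V are the expected score and variance per subject; 1619/0.8 = 2024, against the stated 1994 (1.5% apart).
- Completers: 797.6 × (0.340 + 0.240) = 463, against the stated 462.

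**2. Subjects still on treatment at each visit.** 797.6 × (sum over arms of the proportion without an event before that visit):

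| Week | 38 | 52 | 65 | 78 | 91 | 104 |
|---|---|---|---|---|---|---|
| Subjects | 1595 | 1268 | 1089 | 909 | 745 | 579 |

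At week 104 this is 797.6 × (0.404 + 0.322) = 579.

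**3. Effect of adding country on the standard error.** Nine countries give 8 extra parameters per visit. If country explains a share R² of the residual variance, then with n subjects

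SE ratio = √[(1 - R²) × (n - 3)/(n - 11)].

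The documents give no R², so 0 to 10% is an assumption.

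| Assumed R² | n = 1994 | n = 579 |
|---|---|---|
| 0 | +0.2% | +0.7% |
| 1% | -0.3% | +0.2% |
| 3% | -1.3% | -0.8% |
| 5% | -2.3% | -1.9% |
| 10% | -4.9% | -4.5% |

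For scale, the 95% half-width for HbA1c without country at n = 1994 is 1.96 × 0.85 × 2/√1994 = 0.0746 percentage points. It becomes 0.0748 at R² = 0 and 0.0709 at R² = 10%. The formula treats one visit at a time, so for the MMRM it is an approximation.

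**4. Does the mismatch move the estimate?** This was simulated with 400 trials per setting. The assumptions were equal-sized countries, within-subject correlation 0.5, 20% random early dropout, withdrawal after two consecutive values above 7.0% from week 26, and country R² of 0 to 10%.

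| Model | Mean treatment difference (HbA1c, percentage points) |
|---|---|
| MMRM at week 104, without country | -0.301 to -0.296 |
| MMRM at week 104, with country | -0.302 to -0.296 |
| ANCOVA on last value, with or without country | about -0.14 |

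The gap between MMRM and ANCOVA is about 0.16 points with or without country. Within a single trial, adding country moves the MMRM estimate with an SD of 0.006 to 0.013 points.

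**5. Missing at random: an assumed illustration.** Take two equal country groups with country R² of 5%, an effect of ±0.85 × √0.05 = ±0.19. Early leavers contribute no HbA1c. In one arm dropout is 25% and 15% in the two groups; in the other arm it is reversed. Omitting country shifts the difference by 2 × 0.19 × (0.85 - 0.75)/(0.85 + 0.75) = 0.024 points. With 30% and 10% the shift is 0.048 points. The documents give no sign that such a pattern will occur.

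**The case against.** The strongest reply is that nothing here is an error. The protocol mentions no stratification of randomisation by country, so an MMRM without country is a valid model. These are supportive analyses, and country is not guaranteed to help: at R² = 0 the standard error rises slightly. Country within visit adds 8 parameters at each of eight HbA1c visits, 64 in all, beside an unstructured covariance matrix. Country sizes are not given, fewer than 1,000 subjects are expected from week 78 on, and some countries may be almost empty by week 104. Finally, the SAP defers to a project specification and table shells that are not among the documents, so the covariates finally programmed cannot be confirmed. All of this stands. It limits the size of the point and is why pooling of small countries belongs in the fix. It does not explain why country is in one model of the pair and not in the other.

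A reader might infer that the mismatch would spoil a comparison of MMRM with ANCOVA. The documents do not support that. The ANCOVA uses the last on-treatment value, whenever it was taken. The MMRM uses all visits and targets the effect had everyone stayed on treatment. The two would differ with identical covariates.

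A reader might also extend the point to the responder models that include absence of weight gain, since "The model will include treatment arm as a factor and baseline" HbA1c, without baseline weight. That does not follow. Adding a covariate to a logistic model does not reduce the standard error of the log odds ratio. In simulation it rose from 0.0943 to 0.0969 for an assumed log odds ratio of 0.5 per SD of baseline weight. Adjustment also changes the target to a different conditional odds ratio. The weight component is already defined relative to baseline, and the documents give no evidence that baseline weight predicts the composite.

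**Conclusion.** The point holds as a modest, unexplained inconsistency. Country is in the ANCOVAs for HbA1c, FPG, body weight, BMI and blood pressure and absent from the MMRMs that support them. Adding it changes the standard error of the treatment difference by about +0.2% to -4.9% at 1994 subjects, and by about +0.7% to -4.5% at the roughly 580 expected at week 104. Both ranges rest on an assumed country R² of 0 to 10%; the second also rests on the protocol's own event model. Including country makes the missing-at-random assumption somewhat more plausible, by an amount the documents do not allow one to estimate.

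It would be too strong to call this free precision, because there is a negligible loss if country is not prognostic. It would also be wrong to treat the mismatch as more than a minor contributor to any difference between MMRM and ANCOVA. The primary log rank test uses no covariates, so it and the sample size of 1994 are unaffected.

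**What to change.** State in the SAP that the MMRM for HbA1c, and the corresponding MMRMs for FPG, body weight, BMI and blood pressure, include country as a factor nested within visit, so that their covariates match the ANCOVAs. Add a pre-specified rule for pooling very small countries if the model does not fit. If country is left out on purpose, one sentence giving the reason would do instead.

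The cost is a sentence in the SAP and a minor programming change. Country is already in the analysis datasets, so no new data are needed. The statistical cost is 8 extra parameters per visit.
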